Medications are often the first line of therapy for fibromyalgia, but are frequently associated with adverse effects and show modest treatment benefits in clinical trials and practice.⁷ Aerobic exercise programs have proven benefit, but adherence to exercise is difficult to maintain and can lead to exercise-induced pain and myalgias if performed incorrectly. While the literature supports psychological treatments such as cognitive behavioral therapy (CBT) for reducing the overall symptoms of fibromyalgia, access to therapists with fibromyalgia expertise is limited. For relief, patients often turn to complementary and alternative medicine when traditional treatments are not effective.⁸ Yoga has shown initial promise for relief of fibromyalgia symptoms; presumably because yoga combines the benefits of exercise with relaxation and mindfulness practices. However, few yoga studies in fibromyalgia exist and those conducted have involved small sample sizes and yoga has not been compared to other treatments. With these challenges and limitations in mind, research to develop and compare different treatments for fibromyalgia, especially in veterans, is urgently needed.

We believe other treatment options are needed when pharmacological management fails to relieve fibromyalgia symptoms for veterans. Our long-term research objective is to develop, test, and implement novel treatments that address barriers to effective fibromyalgia treatment and that can be practicably applied in VA care settings. The **Pain Outcomes comparing Yoga versus Structured Exercise (POYSE)** Trial is a 2-arm parallel group, randomized clinical trial. The POYSE trial will target **306 veterans** with fibromyalgia and will compare the effectiveness of a yoga-based intervention (YOGA) with that of a structured exercise program (SEP). The trial will last 9-months and participants will undergo comprehensive outcome assessments at baseline, **1, 3, 6, and 9 months**.

Study Aims:

- 1) **To compare the interventions' (YOGA vs. SEP) effects on overall fibromyalgia severity at 1 month (early response), 3 months (immediate post-intervention) and at 6 and 9 months (sustained effects)**
- 2) **To compare the interventions' effects on specific fibromyalgia symptoms (pain, sleep, fatigue), functional impairment, and related outcomes (quality of life, depression, anxiety)**
- 3) **To compare the cost-effectiveness of the interventions**

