Our primary hypothesis is that the yoga intervention will be more effective than a structured exercise program in reducing overall fibromyalgia severity as measured by the Fibromyalgia Impact

Questionnaire-Revised (FIQR); a global measure of fibromyalgia symptoms.⁹ Our secondary hypotheses is that yoga will be more effective than a structured exercise program in improving secondary outcomes including functional impairment, pain intensity, sleep quality, fatigue, quality of life, depression, and anxiety.

The trial is powered to detect a clinically significant between-group treatment effect. Based on our pilot work and studies from other research groups, we expect both treatment arms to significantly improve fibromyalgia outcomes at all outcome assessment time points (**1, 3, 6, and 9 months**) compared to baseline. In addition to determining whether there is differential clinical effectiveness between the two treatments, their relative cost-effectiveness will be determined.

B. BACKGROUND

B1. Fibromyalgia is common, costly, and associated with frequent health care use

Fibromyalgia affects at least 3%-5% of the general population¹⁰ or approximately 10 million Americans. In clinical populations, the prevalence of fibromyalgia exceeds 15%.¹¹ Women account for more than 80% of affected individuals. The economic burden to society from fibromyalgia-related lost productivity and disability is substantial. Sixteen percent of individuals with fibromyalgia reported receiving Social Security disability payments compared to 2.2% of the non-retirement US adult population.¹² Analysis of administrative claims data from a large, Fortune 100 company showed that the total annual cost for fibromyalgia claimants was \$5,945 versus \$2,486 for other beneficiaries.¹³

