Analytic techniques will be similar to those previously described. Since there will be a number of secondary outcomes, we will account for multiple-comparisons in analyses. We will use the Bonferroni approach to adjust for statistical significance threshold when the number of tests is less than 20. Otherwise, we will use the false discovery rate (FDR)¹²² to control the magnitude of false positives. We will also stratify our analysis based on a baseline depression status (PHQ-9). Our previous research indicated that 30% to 40% of patients will have clinically significant depression, which may adversely affect pain outcomes. Thus, depression is a potential moderator.

D9f. Missing data

Missing data are unavoidable in longitudinal studies. Based on our prior studies, we anticipate a possible dropout rate between 8% and 12%. However, we conservatively estimated a possible 20% drop out rate which is reflected in the sample size calculation. We will first run a logistic model with missing status as the response variable, intervention arm, patients’ demographic characteristics as covariates to check whether the missing status depends on the intervention group assignment and patient characteristics. Second, our linear mixed-effect model can accommodate missing-at-random (or

MAR which is assumed in many trials)¹²³ where no bias will be introduced by ignoring the missing-data mechanism. If drop-outs are Missing Not At Random (MNAR), meaning the likelihood of drop-out depends on an un-observed outcome, and the missing data mechanism is ignored, potential bias can be introduced. We will run sensitivity analyses using complete cases, last observation carried forward imputation, other multiple imputation methods including linear mixed-effect model, to compare results across these analyses to assess the robustness of the inference.

D9g. Economic evaluation

We will conduct cost effectiveness to determine if changes in health care utilization may offset the intervention costs between treatment arms. To conduct this analysis, we will use established methods¹²⁴ to estimate direct costs of the interventions and health care spending for study participants during the **9 month** trial period from the perspective of the VA.

D9h. Costing

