To estimate cost effectiveness, the dependent variable will consist of primary cost outcomes calculated from the VA health care system perspective. Having obtained the relevant VA healthcare utilization events, the healthcare event requires valuation, which is the task of assigning a reasonable market-level dollar for the expense amount. For each patient, outpatient events (visits, procedures, labs, medications, etc.) and inpatient DRGs and medical events (procedures, labs, medications, etc.) will be captured from these patient-specific administrative datasets. VHA databases provide sufficient outpatient and inpatient procedure and associated treatment classifications (by CPT-4, DRG and ICD-9 codes) to allow valuation. [name] has created similar datasets in other VA funded studies and publications. For health care utilization and the associated costs, we will compare inpatient days, outpatient visits, telephone care, number of prescriptions and radiographic tests. However, we may not be able to include inpatient costs because hospitalization may occur rarely during the 9 months of the trial and make estimates of between-group differences imprecise.

We will compare the two treatment arms with respect to total health care costs. Univariate, bivariate and regression techniques for repeated measures will be used to estimate the healthcare events and expenditure amounts. If cost data are skewed, log transformations will be performed prior to performing regression. An ANCOVA model will be used and contain treatment group (independent variable) and adjusted for comorbidities, age, and previous health care cost data collected at baseline as a covariate.

Costs will be reported in current year's dollars. Sensitivity analyses will be used to account for assumptions, including changes in intervention costs and changes in costs related to inpatient or outpatient services. If the interventions are found to be differentially more effective and costly, we will perform a cost-outcome analysis (i.e., incremental cost-effectiveness). We will estimate the effect of the interventions on the primary outcome (FIQR total score). The incremental cost to achieve a clinically meaningful decrease in FIQR total scores due to the interventions, i.e., the cost-effectiveness ratio, is calculated as the difference in intervention costs between the two treatment arms, divided by the difference in effectiveness between groups.

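### D9i plans no measure of sampling uncertainty for the cost-effectiveness ratio itself; the robustness work it names varies cost assumptions, which does not show sampling error

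*Combined protocol and SAP*

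**What the plan says.** Section A lists as its third aim "To compare the cost-effectiveness of the interventions" and adds that, beyond clinical effectiveness, "their relative cost-effectiveness will be determined".

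D9i of the combined protocol and SAP plans three things that bear on this.

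- **Cost.** Total health care costs are compared between arms by an ANCOVA on treatment group, adjusted for comorbidities, age and earlier costs. Costs are log-transformed first if they are skewed.
- **Ratio.** "If the interventions are found to be differentially more effective and costly, we will perform a cost-outcome analysis". The ratio "is calculated as the difference in intervention costs between the two treatment arms, divided by the difference in effectiveness between groups". The formula at the end of D9i has a different numerator: it adds the difference in health care costs to the intervention costs.
- **Robustness.** "Sensitivity analyses will be used to account for assumptions, including changes in intervention costs and changes in costs related to inpatient or outpatient services".

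The FIQR difference comes from the mixed model in D9c, which has random intercepts for patient and for class. D9g says "we will use established methods", but in a sentence about estimating intervention costs and health care spending. The supplied text plans no interval, bootstrap, cost-effectiveness plane, acceptability curve or net-benefit analysis for the ratio.

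**The concern.** The ratio divides one estimated between-arm difference by another. Both carry sampling error, and within patients the two may be correlated. Changing an assumed salary, overhead or service cost moves the numerator by a chosen amount. It does not show how far either difference could move in another sample of the same size.

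The trigger adds to the need. D9i does not say whether the arms are found to differ on point estimates or by a test. A ratio reported because two point estimates fell in the right quadrant may rest on data that fit other quadrants as well.

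Sections C1 and D13 expect the economic evaluation to inform implementation and budget decisions in the VA. A ratio without a measure of precision does not tell those readers how firmly the data support a choice.

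**Working it through.** **Inputs.** From D9a: baseline FIQR 48.3, between-arm difference 14%, SD 17.6, 107 evaluable per arm, ICC 0.02 with 8 per class, 122 evaluable per arm after clustering, 20% attrition. D9i does not say at which visit the FIQR change is taken. I assume 3 months, the primary endpoint.

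**1. The plan's own figures reproduce.**
- Difference: 0.14 × 48.3 = 6.76 (D9a prints 6.79; the gap is immaterial).
- n per arm = 2 × (1.960 + 0.842)² × 17.6² / 6.76² = 106.4, so 107. At 6.79 it is 106. Two-sided t-test power at 107 per arm is 79.9% for 6.76 and 80.2% for 6.79.
- Design effect: 1 + 7 × 0.02 = 1.14; 107 × 1.14 = 121.98, so 122.
- Attrition: 122 / 0.80 = 152.5, so 153 per arm and 306 in total.

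**2. Precision of the denominator, unadjusted.**
- SE = 17.6 × √(2 × 1.14 / 122) = 2.406.
- 95% interval at 6.76: 6.76 ± 1.96 × 2.406 = 2.04 to 11.48.
- With the cost difference treated as known exactly, cost per point runs from 6.76/11.48 = 0.59 to 6.76/2.04 = 3.3 times its point value. The span is 11.48/2.04 = 5.6-fold.

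**3. With baseline adjustment.** D9c adjusts for baseline FIQR. I take SE × √(1 − ρ²), with ρ assumed because the documents give no value.

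| ρ (assumed) | SE | 95% interval at 6.76 | Span |
|---|---|---|---|
| 0 | 2.41 | 2.04 to 11.48 | 5.6 |
| 0.5 | 2.08 | 2.68 to 10.84 | about 4 |
| 0.7 | 1.72 | 3.39 to 10.13 | about 3 |

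**4. The trigger.** Use the unadjusted SE. If the trigger is read on point estimates, an observed difference of 3.4 could meet it. Its interval is −1.3 to 8.1, which includes zero, so the ratio has no bounded interval. If the trigger needs significance, the observed difference must exceed 1.96 × 2.406 = 4.72. At 4.8 the interval is 0.08 to 9.5, and the upper limit on cost per point is very large. Neither reading makes the uncertainty negligible.

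**5. Cost error, illustration only.** The documents give no cost difference and no cost SD. Assume a $500 difference, 153 per arm, independent cost and effect, no design effect on cost, and a FIQR difference of 6.79 with SE 2.41. The point ratio is 500/6.79 = $74 per point. Fieller limits are the values r that satisfy (500 − 6.79r)² ≤ 1.96² × (SE_cost² + r² × 2.41²), with SE_cost = SD × √(2/153).

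| Cost SD (assumed) | SE_cost | 95% limits, $ per point |
|---|---|---|
| 0 | 0 | 43 to 241 |
| 1,000 | 114 | 33 to 251 |
| 3,000 | 343 | −27 to 312 |
| 6,000 | 686 | −150 to 435 |

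These rows show direction only. The argument rests on steps 2 to 4.

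**6. What varying cost assumptions does.** It changes the numerator and leaves the denominator's interval exactly as in step 2 or 3.

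**The case against.** The case on the other side has real content.

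- **The components do have errors.** A reader might infer that Aim 3 would be answered with no measure of uncertainty at all. The documents do not support that. The cost ANCOVA and the FIQR mixed model each yield a standard error, and D9i also compares use of services between arms. The gap is in combining the two. If costs are logged, the ANCOVA error is on the log scale and does not apply directly to the dollar difference in the numerator.
- **The list is open.** A reader might infer that only unit costs will be varied. The sentence is non-exhaustive, and it covers intervention costs and service costs, which can change through use as well as price. But its subject is assumptions, and it commits to no interval.
- **The remark on imprecision is narrow.** D9i says rare hospitalisations may "make estimates of between-group differences imprecise". A reader might take this as conceding that cost differences in general will be imprecise. It is conditional, concerns inpatient costs, and is given as a reason to leave them out.
- **Silence is weak evidence.** D9 does not mention confidence intervals for the primary FIQR contrast either. That is fair. However, a fitted model gives an interval for a contrast as routine output, whereas a ratio taken from two separate models needs a method to be chosen.
- **The ratio is conditional.** It may never be computed. That limits how often the gap bites, but step 4 shows it does not remove it.
- **The 5.6-fold span is the upper end.** It ignores the planned baseline adjustment. This stands.

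**Conclusion.** The point holds for the ratio. Followed as written, D9i would give a cost-effectiveness ratio with variants under other cost assumptions and no measure of its sampling error. From D9a's inputs, the denominator alone spreads cost per FIQR point about 5.6-fold unadjusted, or about 4- to 3-fold at an assumed baseline correlation of 0.5 to 0.7. This takes the true difference to be the planned 6.76 at 3 months, and 122 evaluable patients per arm. Cost error widens this by an amount that cannot be computed from the documents.

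It would be too strong to conclude that the economic comparison is uninformative, or that a 5.6-fold span is what the adjusted analysis would show. The primary FIQR result is not affected. This is a cheap improvement to a stated aim.

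**What to change.** In D9i:

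1. Reconcile the numerator. The text uses the difference in intervention costs, and the formula adds the difference in health care costs. No interval can be built until one definition is fixed. State also the visit at which the FIQR change is taken.
2. Report incremental cost, on the dollar scale, and incremental FIQR effect, each with a 95% interval from a joint bootstrap of patients' cost-effect pairs, resampling classes within arm. D7b expects 15 to 19 yoga classes, so resampling by class is workable there. Say how patients with a missing FIQR are handled, in line with D9f.
3. Show the joint uncertainty, by a cost-effectiveness plane or by net benefit over a range of dollars per FIQR point. The documents give no value per point, so a range is needed and not a single threshold.
4. Do this whether or not the point estimates meet the trigger for the ratio.
5. Keep the cost-assumption sensitivity analyses alongside.

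The cost is some programming and a result that looks less certain. Costs and FIQR are already to be collected for each patient, so no new data or visits are needed.

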The primary outcome measure will be the **Total Score** from the **Fibromyalgia Impact Questionnaire Revised (FIQR)**. The FIQR (**Appendix 4**) has been found to be a useful brief instrument to assess the overall impact and severity of fibromyalgia.⁹⁹ The FIQR is an updated version of the widely used Fibromyalgia Impact Questionnaire (FIQ) which has been extensively used and validated in clinical trials. The FIQR consists of 21-items that assess pain, fatigue, stiffness, sleep, depression, memory, anxiety, balance, and environment sensitivity.^{9,99} All items are framed in the past 7 days and are scored on an 11-point numeric rating scores of 0 to 10, with 10 being "worst." The total score range from 0 to 100, with higher scores representing greater symptom burden and functional limitations from fibromyalgia. The FIQR has strong internal consistency (Cronbach's alpha = 0.79 to 0.93) and is comparable to the original FIQ allowing comparisons between the FIQ and FIQR.¹⁰⁰ In addition to the Total Score, the FIQR contains scales for Symptoms (10 items), Function (9 items), and Overall Impact (2 items); the most important domains in fibromyalgia trials. Scoring of the FIQR involves: 1) summing the score for function (range 0 to 90) and dividing by 3; 2) summing the score for overall impact (range 0 to 20); and 3) summing the score for symptoms (range 0 to 100) and dividing by 2. The three domains are weighted; 30% of total score ascribed to function, 50% to symptoms; and 20% for overall impact.

D8b. Measures, Schedule, and Mode of Administration

In addition to our main outcome measure (FIQR Total Score), we will also measure several other secondary outcomes recommended by the OMERACT guidelines^{97,101} and consonant with the biopsychosocial model at each follow-up assessment. These include depression, anxiety, health related quality of life, pain beliefs, fatigue, sleep, and self-efficacy. These variables are important to assess as key moderators or mediators of intervention effects. Finally, measures of fitness and physical activity as well as measures of **satisfaction and adherence to the interventions** will be assessed. We will also assess the performance of all scales to ensure they meet standard psychometric characteristics.

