cognitive behavioral relaxation techniques and found a 13.6% reduction in FIQR scores. From these studies, we estimate the difference between the yoga and structured exercise group is 17%. A between-group treatment difference of 14% reduction in symptoms represents a minimum clinically meaningful intervention effect.¹¹⁹ To be conservative, we will assume a 14% difference between treatment groups. The absolute score difference at 3 months is estimated to be approximately 7 points (6.79, 14% of 48.3). Assuming a common standard deviation of 17.6 and using a two-sample t-test, we will need 107 evaluable subjects in each arm to detect such a difference with >80% power and 5% Type I standard error rate.

We recognize the correlation of outcomes from subjects within the same yoga or exercise class may reduce the effective sample size compared to the same sample with independent observations. This possible “clustering effect” seen in group delivered interventions has implications for power. We have no preliminary data to estimate the intra-cluster correlation (ICC) for participants within the same group. However, based on similarly designed published studies, we expect the ICC to be relatively small and balanced across the two treatment arms since the cluster sizes will be similar.¹²⁰ Conservatively, we assume an ICC of 0.02 for both treatment groups. With 8 subjects per treatment group/class or cluster, the design effect is $1 + (8-1) \times 0.02 = 1.14$. Therefore, we will inflate our sample size by 14% to accommodate the potential clustering effects. We then need 122 evaluable subjects in each arm. With a conservative 20% attrition, we will then need $(122 \times 2) / 0.80 = 306$ subjects (153 in each arm).

D9b. Data analysis: Baseline characteristics of POYSE sample

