$$\text{Intervention Costs} + (\Delta \text{ Health Care Costs})$$

$$(\Delta \text{ FIQR}_{\text{Yoga}}) - (\Delta \text{ FIQR}_{\text{Structured Exercise Program}})$$

Where Δ FIQR = change in FIQR score, and Δ Health care costs = difference two groups

D10. PROJECT MANAGEMENT PLAN

D10a. Project Timeline

The 1st quarter in year 1 will involve hiring and training personnel. Important steps will include: (1) finalizing treatment protocols for yoga and exercise arms; (2) training the research assistant in screening, enrolling, and consenting study participants; (3) programming the electronic medical records to identify potential study subjects based on fibromyalgia diagnosis; and (4) obtaining permission from individual treating physicians to approach patients of theirs who might be eligible. During the next 2.5 years, we will enroll **306** participants (randomizing **153** to each group). Enrollment will average 10 per month. The **306** participants will be treated for 3 months. Participants will have outcome assessments at baseline, **1, 3, 6, and 9 months**. Thus, enrollment will be conducted from the 2nd quarter (year 1) until the 4th quarter (year 3); the intervention phase from 2nd quarter (year 1) until 1st quarter (year 4); and outcome assessments from 2nd quarter (year 1) until the end of study period. Baseline analysis will begin at the beginning of year 4 and conducted during the final 9 months of the study (separate baseline, 3 month, and end-of-study analyses). Main reports and manuscripts will be prepared in the 3rd and 4th quarters of Year 4.

POYSE Study Timeline																
Quarters	Year 1				Year 2				Year 3				Year 4			
	1	2	3	4	1	2	3	4	1	2	3	4	1	2	3	4
Start-up																
Enrollment																
Intervention																
Assessments																
Analysis																
Manuscripts																

D10b. Overall project coordination and facilities

Overall project coordination will be led by [name] (PI) and [name] (Project coordinator). [name] will coordinate all aspects of the project, trouble-shoot any problems, and provide regular updates on recruitment progress. Drs. [name], [name], and [name] have office, meeting and research space within the HSR&D Center for Implementing Evidence-based Practice (CIEBP) at the RVAMC. [name] and [name] offices are a 5-minute walk or drive, respectively from CIEBP. [name] will be available for the monthly study-related teleconferences.

D10c. Investigator roles

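### The D9i cost-effectiveness ratio gives cost per FIQR point, not per clinically meaningful decrease; its sign convention is undefined and it is computed only conditionally

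*Combined protocol and SAP*

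**What the plan says.** Aim 3 (section A) is to compare the cost-effectiveness of the two interventions. The closing text of section A and the opening of D9g repeat that commitment, and none of the three places attaches a condition.

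D9i does attach one: "If the interventions are found to be differentially more effective and costly, we will perform a cost-outcome analysis". It then names the result, "The incremental cost to achieve a clinically meaningful decrease in FIQR total scores due to the interventions, i.e., the cost-effectiveness ratio", and says that it "is calculated as the difference in intervention costs between the two treatment arms, divided by the difference in effectiveness between groups".

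The displayed formula at the end of D9i has a different numerator: intervention costs (with no difference sign) plus the between-group difference in health care costs. Its denominator is the FIQR change in the yoga arm minus the FIQR change in the exercise arm. The only definition given for the FIQR term is "change in FIQR score".

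Two other sections bear on how to read this. D8a sets the direction of the 0 to 100 scale, "with higher scores representing greater symptom burden and functional limitations from fibromyalgia". D9a gives the only difference that the statistical sections call clinically meaningful: "A between-group treatment difference of 14% reduction in symptoms represents a minimum clinically meaningful intervention effect". It converts this to 6.79 points, or about 7.

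**The concern.** A ratio of dollars to FIQR points is a price per point. The text presents it as the price of a clinically meaningful improvement, which is several points. A reader who trusts the label would take the cheaper figure for the more expensive one.

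The sign is a second source of misreading. In cost-effectiveness work a negative ratio usually suggests that one option dominates. With an undefined direction of change, the trade-off that D9i sets out to price can come out negative, and a dominant option can come out positive.

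Third, if the condition in D9i is not met, the plan compares costs and estimates the FIQR effect but never joins the two, which is what Aim 3 asks for. Sections C1 and D13 offer the economic evaluation as information for VA implementation and budget decisions, so unit, sign and availability all matter to its intended users.

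**Working it through.** **Inputs.** From D9a: baseline FIQR 48.3, meaningful between-group difference 14%, SD 17.6, 107 evaluable per arm. From D9d: responder threshold of more than 30% reduction. From D8a: higher FIQR is worse. The documents give no incremental cost, so 100 to 1,000 dollars per patient is assumed for illustration, with 500 as the worked value. The numerator is taken as net cost, yoga minus exercise.

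**The plan's own figure.** 0.14 × 48.3 = 6.762. The plan prints 6.79, which is 0.4% higher and immaterial here. With 6.79 and SD 17.6, a two-sided 5% t-test at 80% power needs 106.4, hence 107 per arm, as stated. The 6.79 is therefore the difference on which the trial is sized.

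**Unit.** Let C be the incremental cost in dollars and E the difference in FIQR reduction in points. The printed ratio is R = C / E, in dollars per point. The cost of a decrease of M points is M × R. Nothing in D9i supplies M.

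- With M from D9a, the label and the formula differ by a factor of 6.76 (calculated), 6.79 (printed) or 7 (rounded).
- This factor does not depend on C, E or the sign. For example, take the reductions printed in D9a (31% and 13.6%) at face value: E = (0.31 − 0.136) × 48.3 = 8.40. Then C = 100 to 1,000 gives R = 11.90 to 118.99 dollars per point, against 80.79 to 807.93 dollars per 6.79 points.
- If the meaningful decrease were instead the D9d responder threshold, M = 0.30 × 48.3 = 14.49 and the factor would be about 14.5. D9d does not call that threshold clinically meaningful, and D9i does not say which applies.

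**Sign.** Take a difference of 6.79 points and a cost difference of 500 dollars; 500 / 6.79 = 73.64.

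| Yoga compared with exercise | Change = follow-up minus baseline | Change = reduction |
|---|---|---|
| Better, costlier | −73.64 | +73.64 |
| Better, cheaper | +73.64 | −73.64 |
| Worse, costlier | +73.64 | −73.64 |
| Worse, cheaper | −73.64 | +73.64 |

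The first and last rows are the cases in which one arm is both more effective and more costly, so they are the cases for which D9i plans the ratio. Under follow-up minus baseline both are negative; under reduction both are positive. The documents use both conventions: B11 writes an FIQR improvement as −30.7%, while D9a and D9d speak of reductions.

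**Condition and numerator.** Set side by side, Aim 3 and D9g are unconditional and the ratio in D9i is conditional, with no statement of what counts as having found a difference. The text of D9i puts only the difference in intervention costs on top; the formula adds the difference in health care costs and shows intervention costs undifferenced. These are different numerators.

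**The case against.** The strongest reply is that these are matters of wording in a secondary analysis, and that a sensible analyst would resolve them.

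- **On sign.** A reader might infer that the plan has the wrong sign, or that the ratio turns negative whenever yoga is better. The documents support neither. D9i calls the denominator a difference in effectiveness, which allows change to mean reduction, and then the sign is right. Even under follow-up minus baseline, a better and cheaper yoga arm gives a positive ratio. This objection stands: the direction is undefined rather than wrong.
- **On misreading.** Because the ratio is planned only for a trade-off, a reader who knows the condition would not mistake a negative value for dominance. That is fair while the condition remains. It no longer protects the reader once the ratio is reported unconditionally.
- **On unit.** D9i does not define its meaningful decrease, and the 14% in D9a is a between-group difference. The factor of about 7 therefore depends on carrying D9a across. The mismatch itself does not, since no reading of the formula turns dollars per point into dollars per meaningful decrease.
- **On the condition.** D9i compares total health care costs whatever happens, and D9c always estimates the FIQR contrast, so Aim 3 would not be empty. A reader might also infer from the stated power of just over 80% that the ratio would be missing in about one trial in five. That does not follow: D9i does not equate a finding with statistical significance, the condition also requires higher cost, and D9a's power is for a t-test, whereas D9c plans a repeated-measures ANCOVA that it describes as more powerful when baseline and follow-up are positively correlated.

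**Conclusion.** The point holds in four limited parts.

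1. The label and the formula describe different quantities. The labelled one is about 7 times larger if D9a's 14% is the meaningful decrease.
2. The direction of FIQR change is undefined. Under the usual follow-up minus baseline reading, the ratio is negative when yoga is better and costlier and positive when yoga is better and cheaper.
3. Making the ratio conditional conflicts with the unconditional promise of Aim 3 and D9g. Costs would still be compared, but might not be joined to effect. How often this would happen cannot be derived from the documents.
4. The text and the formula in D9i disagree on the numerator.

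The dollar figures above are illustrations on assumed costs; only the scale factor and the sign pattern are conclusions. The effect is confined to Aim 3. The primary FIQR analysis and the sample size are untouched. The section should be corrected before the economic analysis is run.

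**What to change.** Revise D9i as follows.

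- Define effectiveness as FIQR reduction, baseline minus follow-up, at a named time point. Three months matches the primary endpoint, but D9g accrues costs over 9 months, so the choice must be justified against that period.
- Use reduction in the yoga arm minus reduction in the exercise arm as the denominator, and state that the cost difference runs in the same direction.
- Call the result incremental cost per 1-point FIQR reduction. To keep the present label, multiply by a stated meaningful difference (about 7 points on D9a's figures) and say that this is the between-group value from D9a, not the responder threshold of D9d.
- Reconcile the numerator: state whether it is the difference in intervention costs alone or that difference plus the difference in health care costs, and make text and formula agree.
- Remove the condition. Report incremental cost and incremental FIQR reduction with their joint uncertainty whatever the primary result, since a ratio alone is unstable when the effect difference is near zero and ambiguous when its sign is uncertain.

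The cost is a change of wording and formula in one section and a modest amount of extra analysis. All the FIQR and cost data required are already planned for collection.
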